4.3 Replacement

Patients who discontinue due to a DLT in Cycle 1 will not be replaced.

Patients who discontinue during Cycle 1 due to any reason other than a DLT and patients who were non-compliant in Cycle 1 will be replaced for the purpose of Cycle 1 DLT determinations, but may continue on the study at the discretion of the investigator. Non-compliance is determined by the investigator and can include failure to take medications or failure to have study-related activities performed.

Patients who took less than 21-days of the required dose of study drug during Cycle 1 will be replaced for the purpose of Cycle 1 DLT determinations, but may continue on the study at the discretion of the investigator.

Patients with insufficient PK data may have to be replaced. The decision to replace a patient due to insufficient PK data will be taken on a case-by-case basis after consultation between the investigator and the sponsor.

Patients who discontinue after Cycle 1 will not be replaced.

If the dropout rate in any expansion cohort is $\geq 20\%$, additional patients may be enrolled to ensure that at least 20 patients per indication will be evaluable for the response assessment.

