3.4 Part A Dose Escalation Schedule and Treatment Schema

Oral PCLX-001 will be provided as continuous daily dosing on a 28-day cycle. The starting dose of PCLX-001 will be 20 mg daily (Section 3.1.1). Dose escalation will follow a modified Fibonacci design such that the magnitude of escalation decreases as the dose level nears the human equivalent dose (HED) of the HNSTD in dogs and then escalate at 1.4 times the previous dose until MTD or RP2D is reached.

The dose level schedule is as below (1 cycle = 28 days):

Dose Level**	Daily Oral Dose (mg)	Number of Capsules	
		10 mg	70 mg
-1	10	1	0
1 (starting dose)*	20	2	0
2	40	4	0
3	70	0	1
4	100	3	1
5	140	0	2
6	210	0	3
7	280***	0	4

* Trial will start at Dose Level 1 and will de-escalate to Dose Level -1 if DLT is observed.

** If ≥ 2 out of 6 DLTs are observed in Dose Level -1, 1 or 2 then consideration will be given to changing dosing schedule (eg. 28-day schedule with each week comprising 4 days on medication and 3 days off medication).

*** If DLT is not observed at the dose of 280 mg, the dose will be considered the MTD. If required, the MTD cohort may be expanded by an additional 10 patients for further toxicity and response assessment.

For each dose-escalation cohort, treatment with the first dose of PCLX-001 will be staggered such that the second participant enrolled in the cohort will receive PCLX-001 at least two weeks after the first participant and all subsequent participants at least one week after the previous participant.

Each participant will be treated with the dose of PCLX-001 they are assigned to, until the occurrence of a DLT or other study stopping point occurs, at which point the dose of PCLX-001 will be modified as per protocol or study drug administration will be discontinued.

If DLT occurs at Dose Level 1, a safety meeting will occur to determine the feasibility of continuing the study at Dose Level -1. Alternative dose schedules may also be considered if DLTs occur during Dose Levels, -1, 1 or 2.

Participants who experience a DLT or have received at least 21 days of PCLX-001 during cycle 1 will be evaluable for toxicity. If a participant does not meet these criteria, the participant may be replaced (Section 4.3).

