5.3.1 Cycle 1 DLT Modifications for Part A Dose-Escalation Cohorts

If a patient experiences a treatment related hematological or non-hematological DLT (as defined in Section 3.2) during Cycle 1, the next dose of PCLX-001 will be delayed for up to 28 days for Part A. If the toxicity fails to resolve to CTCAE Grade ≤ 2 within 28 days, the patient should be withdrawn from study treatment but followed for safety until resolution.

If the toxicity resolves to CTCAE Grade ≤ 2 , re-treatment with PCLX-001 can be considered. Re-treatment of this patient should be at 1 dose level below the initial dose. Detailed dose modifications are described in Table 5-1. Patients experiencing any drug-related, clinically significant, non-hematological CTCAE Grade 4 toxicity will be withdrawn from study treatment but followed for safety until resolution. There will be no intrapatient dose escalation and no more than two dose reductions will be allowed.

Table 5-1: Dose Modifications of PCLX-001

Existing Dose (mg)	Modified Dose (mg)
280	210
210	140
140	100
100	70
70	40
40	20
20	10
10	Discontinue study drug

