5.5 Treatment Compliance

PCLX-001 will be dispensed to patients to be taken orally on an ambulatory basis as well as during clinic visits.

During ambulatory treatment, patients will document the intake of PCLX-001 in a compliance diary.

Unused PCLX-001 study drug will be returned by patients. The time and amount of study drug intake will be recorded in the compliance diary. Each patient's compliance will be evaluated by the study center. This information will be transferred into the eCRF taking into account each dose interruption and / or any changes in dosing.

To ensure the required number of patients are evaluable Cycle 1 DLT dose-escalation cohorts, participants will need to have received at least 21-days of the planned total dose (unless a DLT occurs). Patients non-compliant in Cycle 1 will be replaced.

Any discrepancies between actual and expected amount of returned study medication must be discussed with the patient at the time of the visit, and any explanation must be documented in the source records.

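### The 21-day replacement rule in Section 4.3 has no DLT exception, so it conflicts with Sections 3.4 and 5.5 for a Cycle 1 DLT patient who is held and re-treated

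*Combined protocol and SAP*

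**What the plan says.** Four sections of the protocol decide who counts towards the Cycle 1 DLT rate.

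- **Section 3.4:** "Participants who experience a DLT or have received at least 21 days of PCLX-001 during cycle 1 will be evaluable for toxicity". Replacement arises only when neither condition holds: "If a participant does not meet these criteria, the participant may be replaced", with a pointer to Section 4.3.
- **Section 5.5** repeats the 21-day test with an exception: "participants will need to have received at least 21-days of the planned total dose (unless a DLT occurs".
- **Section 4.3** has two separate sentences. The first is "Patients who discontinue due to a DLT in Cycle 1 will not be replaced". The second is "Patients who took less than 21-days of the required dose of study drug during Cycle 1 will be replaced", and it adds that these patients may stay on study if the investigator agrees. The second sentence does not mention DLTs.
- **Section 8.2** defines the MTD-determining population as patients who kept to the regimen laid down in the protocol and had their scheduled safety evaluations, or who stopped early because of a DLT.

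Section 5.3.1 governs treatment after a Cycle 1 DLT: "the next dose of PCLX-001 will be delayed for up to 28 days for Part A". If the toxicity resolves sufficiently, treatment may resume: "Re-treatment of this patient should be at 1 dose level below the initial dose".

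**The concern.** A patient who has a Cycle 1 DLT, is held, and resumes at the lower level has not discontinued, so the protective sentence in 4.3 does not apply. If that patient ends Cycle 1 with fewer than 21 qualifying days, 4.3 says replace, while 3.4 and 5.5 say evaluable. Section 8.2 does not settle the matter. Its DLT limb covers only those who stopped early, and it does not say whether a hold and reduction under 5.3.1 counts as keeping to the regimen.

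The MTD is a primary objective and rests on three to six patients per level, where a single DLT decides the next step. If the literal 4.3 sentence is followed and the DLT leaves the count, the error always runs towards escalation, in a first-in-human trial.

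**Working it through.** **Stated size.** Section 8.1 gives 9 to 52 patients for Part A. Seven levels × 6 + 10 for the MTD expansion = 52, and 3 + 6 = 9. The totals reproduce, although this derivation is inferred. The conflict does not depend on them.

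**Can the case arise?** A cycle is 28 days (Section 3.4), and missed doses are not made up (Section 5.2). Let *k* be the day of the first missed dose and *h* the number of held days inside Cycle 1.

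1. *Any dose counts towards the 21 days.* Dosing days = 28 − *h*. With *h* = 7 this is 21, which passes; with *h* = 8 it is 20, which fails. Fitting eight held days into the cycle needs *k* + 7 ≤ 28, so *k* ≤ 21.
2. *Only days at the assigned dose count.* Section 4.3 does not define the required dose. After re-treatment one level lower, qualifying days = *k* − 1. With *k* = 21 this is 20, which fails; with *k* = 22 it is 21, which passes.

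Example: first missed dose on Day 15, eight days held, six days at the reduced dose. That gives 14 + 6 = 20 dosing days, of which 14 are at the assigned dose. The patient fails on either reading.

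Footnote a in Section 3.2 shows how near the limit the protocol already runs. Grade 4 neutropenia becomes a DLT when the interruption lasts 7 days or more. Seven held days in Cycle 1 leave exactly 21, so one more missed day fails the 4.3 test.

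**Effect on the counts.** This applies only if the replaced patient's DLT is dropped and the replacement has none:

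- 1/3 reads as 0/3: escalate without the three extra patients.
- 2/6 (33%, stop) reads as 1/6 (17%, escalate).

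**Illustration.** Under the Section 3.3 rule, with DLT probability *p*,

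P(escalate) = (1 − *p*)³ + 3*p*(1 − *p*)² × (1 − *p*)³.

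At *p* = 0.33: 0.67³ = 0.301 and 3 × 0.33 × 0.67² = 0.444, so P = 0.301 + 0.444 × 0.301 = 0.434.

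If a share *f* of DLT patients is replaced and not counted, the DLT probability among counted patients is *p′* = *p*(1 − *f*)/(1 − *pf*). At *p* = 0.33 and *f* = 0.5: 0.165/0.835 = 0.198, giving P = 0.714. The documents give neither *p* nor *f*; both are assumed.

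| True DLT rate | All DLTs counted | *f* = 0.25 | *f* = 0.5 |
|---|---|---|---|
| 0.25 | 0.600 | 0.709 (*p′* = 0.200) | 0.828 (*p′* = 0.143) |
| 0.33 | 0.434 | 0.557 (*p′* = 0.270) | 0.714 (*p′* = 0.198) |
| 0.40 | 0.309 | 0.428 (*p′* = 0.333) | 0.600 (*p′* = 0.250) |

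**The case against.** The best answer is that the rule is already right elsewhere. Section 3.4 makes any DLT patient evaluable and sends to 4.3 only those who meet neither criterion, so on that route a DLT patient never reaches the 21-day sentence. Section 5.5 carries the exception. Section 4.3 does not say that an observed DLT is discarded, and Section 3.3 stops escalation once two patients at a level have any DLT, whether or not they were replaced. Before a new level opens, Section 3.1 requires review of data from all patients at the current level, Section 11.2 supplies those data, and Section 10.5 holds accrual for related SAEs and Grade 3 or higher events. On 8.2, Section 3.4 provides that after a DLT "the dose of PCLX-001 will be modified as per protocol or study drug administration will be discontinued", which supports treating a hold and reduction as part of the regimen. The affected group is also narrow: it leaves out patients who discontinue and those whose first missed dose falls after Day 21, and re-treatment is optional.

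Most of this stands as evidence of intent. It makes a lost DLT less likely and limits 8.2 to an ambiguity. It also means that the probabilities above describe only the reading in which the DLT is dropped. It does not remove the conflict. Section 3.4 names 4.3 as the place to look for replacement, and there the sentence says that such patients will be replaced, without exception. The accrual hold and the cohort review do not define who is in the DLT denominator.

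**Conclusion.** The concern holds. For a Cycle 1 DLT patient who is held and re-treated with fewer than 21 qualifying days, Section 4.3 read literally contradicts Sections 3.4 and 5.5, and Section 8.2 leaves the case open. At its largest, the effect on a cohort is one DLT removed from a count of three or six, which is enough to change an escalation decision. At an assumed true DLT rate of 33%, the chance of escalating would rise from 0.43 to 0.56 or 0.71 if a quarter or a half of DLT patients were replaced. Those figures require that the literal sentence is followed and that the replaced patient's DLT is dropped. The rest of the protocol suggests that neither is intended. The text should give one answer before the first cohort is read.

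**What to change.** 1. In Section 4.3, add to the 21-day sentence: *unless a DLT occurred*.
2. In Section 8.2, replace the limb for patients who stopped early because of a DLT with: *who experienced a DLT in Cycle 1, whether or not re-treated*.
3. State one evaluability definition and use it in 3.4, 4.3, 5.5 and 8.2. It should carry one wording of the 21-day test, which now refers variously to days of drug, of the required dose and of the planned total dose, and should say whether days at a reduced dose count. It should also cover the non-compliance replacement sentences in 4.3 and 5.5, which have no DLT exception either.

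Two minor additions would help. Settle whether such patients may or will be replaced. Report toxicity-related replacements by dose level, with the safety review recording whether each was judged a DLT under Section 3.2. Which toxicities are dose-limiting remains a clinical decision.

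The cost is wording in four sections and, if the minor point is taken up, one descriptive table. No patients are added, and the DLT definition, the hold rule and the doses do not change.

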3. STUDY DESIGN

3.1 Overview of Study Design

This is a phase I dose-escalation, safety and tolerability study of oral PCLX-001, conducted in a multicenter, non-randomized, open-label, non-controlled design. The study is comprised of two parts: Part A (single-agent dose escalation) and Part B (single-agent expansion cohorts).

For Part A dose-escalation, patients will be accrued in cohorts of 3 to 6 patients to each dose level. A new dose level cannot open to accrual until toxicity has been determined in the preceding dose level (i.e. all patients have completed their first cycle of therapy and data for all patients in that dose level have been reviewed at a safety cohort review meeting). Six patients will be treated at the maximum tolerated dose (MTD) and/or recommended phase II dose (RP2D). If required, the MTD cohort may be expanded by an additional 10 patients for further toxicity and response assessment. The MTD cohort expansion may be restricted to B-cell lymphoma or advanced solid tumours to ensure there is proper distribution during dose escalation.

For Part B (single agent expansion cohorts), two expansion cohorts (N=20 each) will be opened to determine the preliminary clinical activity of PCLX-001. The Part B dose expansion Cohort A will occur once MTD and RP2D has been determined. Part B dose expansion Cohort B will occur once dose escalation has achieved a dose that has both acceptable safety and achieves drug exposures predicted to have activity in R/R B-cell lymphomas.

Expansion Cohort A: Participants with advanced solid malignancies showing preclinical sensitivity or molecular markers of sensitivity to PCLX-001. This includes breast, non-small cell lung (NSCLC), small-cell lung (SCLC), colorectal (CRC), and bladder cancers

Expansion Cohort B: Participants with relapsed/refractory (R/R) B-cell lymphoma: diffuse large B-cell lymphoma (DLBCL), high grade B-cell lymphoma (HGBL), follicular lymphoma (FL), mantle cell lymphoma (MCL), and Burkitt lymphoma. Transformed large B-cell lymphoma will also be included.

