3.5 Design of Part B Expansion Cohorts

Once the MTD has been defined, preliminary activity will be further evaluated in the expansion part of the study. If clinically indicated, separate cohort(s) may be open for enrollment to evaluate a different schedule of PCLX-001 (for example a break within cycles), based on safety, PK and preliminary activity data and integrated PK/efficacy and PK/safety modelling from the dose escalation. The RP2D will be defined by the sponsor in conjunction with the investigators after reviewing the data from all parts and stages of the study, including available PK data and intensity of adverse events (AEs), and efficacy parameters, including overall response rate (ORR). The RP2D may be the MTD but not necessarily as not only safety data will be taken into account prior to its determination.

Two expansion cohorts will be opened to determine the preliminary clinical activity of PCLX-001. Part B dose expansion Cohort A will occur once the MTD and the RP2D are determined by the sponsor and investigators after data review.

Part B dose expansion cohort B will occur once dose escalation has achieved a dose that has both acceptable safety and achieves drug exposures predicted to have activity in R/R B-cell lymphomas. See Appendix D for the background, rationale, and determinants of the decision to open dose expansion cohort B.

- Expansion Cohort A: 20 participants with advanced solid malignancies showing preclinical sensitivity or molecular markers of sensitivity to PCLX-001: breast, non-small cell lung, small-cell lung, colorectal, and bladder cancers
- Expansion Cohort B: 20 participants with relapsed/refractory (R/R) B-cell lymphoma: diffuse large B-cell lymphoma (including transformed disease), high grade B-cell lymphoma, follicular lymphoma, mantle cell lymphoma, and Burkitt lymphoma.

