8. STATISTICAL CONSIDERATIONS

8.1 Sample Size Determination

The exact sample size for Part A dose-escalation cannot be pre-determined and depends on the number of cohorts needed to reach MTD. Part A will enroll at least 9 patients and up to 52 patients. In Part B, there are two expansion cohorts of 20 patients each for a total of 40 patients.

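### The Part B top-up rule in section 4.3 uses an undefined unit and does not secure its aim of 20 response-evaluable patients; separately, Table 8-1 leaves early losses out of the response rate

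*Combined protocol and SAP*

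**What the plan says.** Section 8.1 sizes Part B in one sentence: "In Part B, there are two expansion cohorts of 20 patients each for a total of 40 patients". Section 3.1 agrees ("two expansion cohorts (N=20 each) will be opened to determine the preliminary clinical activity of PCLX-001"), and so does section 3.5, which gives 20 to each cohort. Each cohort is a pool. Cohort A takes breast, non-small cell lung, small-cell lung, colorectal and bladder cancer; Cohort B takes five named lymphoma histologies.

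The last paragraph of section 4.3 adds a provision for the expansion cohorts. Its trigger is a dropout rate of at least 20% in any expansion cohort. Its purpose is a different quantity: "additional patients may be enrolled to ensure that at least 20 patients per indication will be evaluable for the response assessment". Neither dropout nor indication is defined. Immediately before it stands a general sentence: "Patients who discontinue after Cycle 1 will not be replaced". The other replacement rules in that section serve the Cycle 1 DLT determination or, case by case, missing PK data.

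Two further places matter. Section 7.3 puts the first on-treatment tumour assessment at the end of Cycle 2. Table 8-1 (section 8.2) admits to the efficacy population only treated patients with at least one on-treatment tumour assessment.

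**The concern.** A top-up rule that aims at a number of evaluable patients should deliver that number, or say when it will not. This one acts only above a threshold, so a cohort with little dropout can end with fewer evaluable patients than a cohort with more. Its target is expressed in a unit that the sizing sections do not use. It is also unclear whether a patient who leaves during Cycle 2, before the first scan, may be made good at all.

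At stake is the denominator for anti-tumour activity. That is the secondary objective (section 2) and the stated purpose of Part B (section 3.1). Section 3.5 also lists overall response rate among the data used to set the RP2D, so the way early losses are counted affects more than a descriptive table.

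**Working it through.** **1. The plan's own figure.** 2 cohorts × 20 = 40, which agrees with section 8.1. That section gives no target response rate, precision goal or dropout allowance, so the 20 itself cannot be derived.

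**2. The trigger.** With 20 enrolled and k dropouts, top-up is available when k/20 ≥ 0.20, that is, k ≥ 4. If every dropout is non-evaluable, 20 − k remain.

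| Dropouts k | k/20 | Evaluable | Top-up |
|---|---|---|---|
| 0 | 0% | 20 | not needed |
| 1 | 5% | 19 | no |
| 2 | 10% | 18 | no |
| 3 | 15% | 17 | no |
| 4 | 20% | 16 | optional, to 20 |

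**3. How often the gap would arise.** The documents state no dropout rate, so I assume a range. With K ~ Binomial(20, d), the chance of 1 to 3 dropouts (fewer than 20 evaluable, trigger not reached) is 63% at d = 5%, 75% at 10%, 61% at 15% and 40% at 20%. To expect 20 evaluable, enrolment would have to be 20/(1 − d), rounded up: 22, 23, 24 and 25 patients for the same four rates.

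**4. Precision.** With no responses, the exact two-sided 95% upper limit is 1 − 0.025^(1/n): 16.8% at n = 20 and 19.5% at n = 17, a difference of 2.7 percentage points. With 4 responses the Clopper-Pearson interval is 5.7% to 43.7% at n = 20 and 6.8% to 49.9% at n = 17.

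**5. The two sentences in section 4.3.** A patient who stops in Cycle 2 before the first scan has discontinued after Cycle 1, so the general sentence bars replacement. The same patient normally has no on-treatment assessment, so Table 8-1 makes that patient non-evaluable, which is the loss the top-up exists to repair. The text does not say which sentence governs.

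**6. The denominator.** Let p be the response probability in treated patients and e the probability of having an on-treatment scan. Responders necessarily have one, so the rate in the efficacy population is p/e, which is at least p. Example with assumed counts: 20 treated, 3 lost before the scan and 4 responders give 4/17 = 23.5% under Table 8-1, against 4/20 = 20.0% in all treated.

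**7. Does top-up add to this?** Patients added under the same eligibility and evaluability rules have the same p and e, so p/e is unchanged. At e = 0.80, the ratio of treated to evaluable is 20/16 = 1.25 before a refill and 25/20 = 1.25 in expectation after it. Top-up changes n, not the bias.

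**The case against.** Much can be said for the plan. The stated total is correct. The top-up is worded as permission, so 20 evaluable is an aim and the plan does not break a promise. The sentence about leaving after Cycle 1 follows paragraphs mainly about DLT evaluation, a Part A matter, and the next sentence is specific to the expansion cohorts and speaks of additional patients rather than replacements; the two can be read together. Part B has no hypothesis test or response threshold that depends on 20 evaluable patients. A patient who leaves after the Cycle 2 scan remains evaluable, so not every dropout costs a patient. All of this stands, and it keeps the point modest.

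Four stronger readings are tempting and should not be drawn:

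- *The plan needs 200 patients.* Five types per cohort at 20 each would give 100 per cohort and 200 in all, against 40. But the same sentence sets its trigger by expansion cohort, 20 is exactly the cohort size, and no section sizes by tumour type. The natural reading is an imprecise word.
- *The rule guarantees 17.* It does not. Because top-up is optional, 4 or more dropouts can leave 16 or fewer, so there is no floor.
- *Top-up inflates the response rate.* The inflation comes from the Table 8-1 definition, with or without added patients.
- *Power is lost or type I error is raised.* Part B has no test to which either could apply.

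What the objection does not remove is the undefined unit, the threshold that works against the stated aim, the two unreconciled sentences, and the exclusion of early losses from the efficacy population.

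**Conclusion.** The point holds as a clarification worth making before Part B reports. Section 4.3 states an aim of 20 evaluable patients in a unit that the sizing sections do not use, and its optional, threshold-based top-up does not secure it: 1 to 3 losses leave 19 to 17 evaluable with no top-up, while 4 or more may be refilled. These counts assume 20 enrolled and every dropout non-evaluable. The probabilities in the working also rest on assumed dropout rates. The cost in precision is small.

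The upward bias from Table 8-1 is separate and matters more for interpretation, because section 3.5 uses response rate in choosing the RP2D. Its size is the ratio of treated to scanned patients: 20/17 = 1.18 in the 15% example. It applies to the extent that patients leave before a scan because of progression, death or toxicity. A patient whose early progression is documented on an unscheduled scan would stay in the denominator.

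**What to change.** 1. In section 4.3, replace the reference to indication with cohort, and define dropout for this purpose as not evaluable for response.
2. State 20 per cohort as the number treated, with no commitment to 20 or to 17 evaluable.
3. Report response in all treated patients, by amending Table 8-1 or adding this analysis beside it. Count patients lost before the first scan to progression, death or toxicity as non-responders, and state in advance how those lost for other reasons are handled.
4. Limit any top-up to patients who are non-evaluable for those other reasons.
5. State that the sentence on discontinuation after Cycle 1 applies to DLT evaluation in Part A, or reconcile it with the top-up in some other way.

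The cost is protocol wording, a slightly lower reported response rate and a slightly less favourable stated evaluable number. No extra patients are needed.
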